## 2.5 Participant timeline

Enrollment of adolescent girls will take place in October 2019, at the time of baseline survey. Interventions were planned to be implemented for a single school year (approximately 7 months), from October 2019 (when the school year/regular school classes begin) to May-June 2020 (when the regular school classes end for the school year).

In March 2020, the World Health Organization declared COVID-19 a pandemic. School closures and disruptions to work and field conditions in Ethiopia resulted in program implementation being halted in March 2020. Trainings for school principals, teachers and HEWs re-initiated in November 2020, and interventions will be implemented through the first school semester. Adolescent girls will be assessed at endline in March-April 2021.

## 2.6 Sample Size

The primary study sample is adolescent girls enrolled in primary school and aged 10-14 years (grades 4-8). The sample size was estimated based on current prevalence of the primary outcome, the expected change after intervention, power to detect those differences (80%), and level of significance ( $\alpha=0.05$ ). As the intervention was randomized at the cluster level (54 clusters) rather than the individual level, cluster effect was considered for sample size calculation.

We used the number of food groups from the A&T Phase 1 endline survey for SNNPR (mean: 3.26, SD: 1.40, categorized as 9 food groups; Arimond et al., 2010), assuming an intra-cluster correlation (ICC) of 0.18. We calculated that a minimum sample of 189 girls per group will be able to detect a minimum of 0.6 food group consumption increase. The sample size at endline will be rounded to 270 girls per group so that 10 girls per school (2 per grade) will be sampled. Based on baseline data, we observed a mean of 3.69, SD: 1.56, categorized as 10 food groups. Assuming an ICC of 0.015, we estimated that this sample size will detect a minimum difference of 0.5 food groups.

School principals, science teachers and HEWs responsible for providing nutrition education or facilitating other related activities/interventions will also be included in both baseline and endline surveys.

At baseline, a light data collection at schools and subsamples of adolescent girls and their parents will be conducted to assess comparability between study arms. At endline, the full samples of adolescent girls and their parents will be surveyed (including those who participated at baseline).

Thus, the overall study samples are presented in **Table 3**.

Table 3. Sample sizes

	Baseline 2019		Endline 2021	
	Intervention	Control	Intervention	Control
Adolescent girls	81	81	270	270
Parents of adolescents	81	81	270	270
Principals (1 per school)	27	27	27	27

Science teachers (1 per school)	27	27	27	27
HEWs (1 per school)	27	27	27	27
Total	243	243	621	621

## 2.7 Recruitment

Study participants will be sampled using a school-based sampling strategy. Lists of eligible adolescent girls will be taken from primary school enrollment registries. Enrollment typically begins in late September and continues for roughly two weeks after school begins to accommodate for any delays. Enrollment records (available at the time of the survey) will be used to verify the birthdate/age of eligible students, which may be recorded from birth certificates or self-reported. Then, adolescent girls will be randomly selected by simple random sampling until the required sample size is reached and visited at home to be recruited and interviewed.

## III. Methods: Assignment of Interventions

### 3.1 Allocation

A cluster is defined as the primary school that includes grades 1-8. Four woredas in SNNPR (with 31 schools) and three woredas in Somali region (with 23 schools), i.e., one school under each woreda school supervisor, were selected as potential intervention areas (see **Figure 3**). (Within woredas, there are designated supervisors at the education office who are responsible for supervising 1-7 schools. Supervisors are responsible for visiting schools one day per week (less frequently in the Somali region) and are provided with a checklist to ensure that schools are operating effectively. As feasible, we tried to select one school under the responsibility of a (unique) supervisor, to avoid study contamination and confusion among supervisors in conducting their duties.) The samples across the two regions will be pooled to estimate effects at program level. We will use stratified randomization within woreda to try to balance potential co-interventions and confounders. Then 27 schools will be allocated to the intervention arm and 27 schools will be allocated to the control arm by use of computer-generated pseudo-random numbers.

### 3.2 Blinding (masking)

This evaluation study will be unblinded. Adolescents in the intervention areas will not be informed about the results of the randomization. However, there will be no blinding of the interventions at schools or other points of service delivery.

## IV. Methods: Data Collection, Management and Analysis

### 4.1 Data collection methods

[figure not shown]
Data will be collected at the primary school and household levels, using pretested questionnaires. The following set of tools will be translated from English to Ahmaric and used during the baseline and endline surveys:

- i. Primary school observation checklist
- ii. Teacher/Principal questionnaire
- iii. Health Extension Worker (HEW) questionnaire
- iv. Adolescent girl questionnaire

v. Parents questionnaire

Topics included in each of the data collection methods are presented in **Table 4**.

Figure 2. Trial flow

**Note:** The baseline and endline surveys will include cross-sectional interviews of adolescent girls, as well as their parents, school principals, science teachers, and HEWs.

Table 4. Data collection methods and topics

Data collection method	Topics included
Primary school observation checklist	Infrastructure, WASH, supplies, food environment, and nutrition education materials (e.g. posters) and displays
Teacher/Principal questionnaire	Teacher/principal background, school role, nutrition-related activities/interventions, perceptions/beliefs, nutrition knowledge
HEW questionnaire	HEW background, school and community role, nutrition-related activities, perceptions/beliefs, nutrition knowledge
Adolescent girl questionnaire	Adolescent background, school attendance, meal and snacking patterns, home food environment, nutrition knowledge, WASH practices, social desirability, parental interaction and other influencers (including sharing education messages and materials), gender and marriage beliefs and decision-making power
Parent questionnaire	Household roster, social involvement, exposure to nutrition information, dietary diversity, nutrition knowledge, gender and marriage beliefs and decision-making power, social desirability, home food environment, food security, dwelling and assets

#### 4.1.1 Primary school observation checklist

A school observation checklist will be included to obtain information on the infrastructure of the school, supplies and materials, food environment and student enrollment.

Table 5. Description of topics to be included in the primary school observation checklist

Module	Topic	Description	Respondent
1	School identification	Location and school supervisor	Enumerator
2	Infrastructure	School amenities and condition	Enumerator (direct observation)
3	Supplies, materials and records	Availability of desks, books, textbooks, pens/pencils, computer, nutrition materials, etc. and records of nutrition activities, PTA meetings and community events	Enumerator (direct observation and taken from school records)
4	Food environment	School canteen, availability of food items, food points off school grounds	Enumerator (direct observation)
5	School hours and size	School hours, break times, and number of students and teachers	Enumerator (taken from school records)
6	Student enrollment and attendance	Attendance and school records of adolescent girls participating in the study	Enumerator (taken from school records)

#### 4.1.2 Teacher/Principal questionnaire

Interviews with principals and science teachers at the primary schools will gather information on the individual's role at the school, nutrition-related activities/interventions, nutrition knowledge, exposure to training, and supervision.

Table 6. Description of modules in the teacher/principal questionnaire

Module	Topic	Description	Respondent
1	Identification	School and respondent type	Enumerator
2	Demographic characteristics	Age, gender, education, language, years of experience	Teacher/Principal
3	School role	Position, years worked at the school, class(es)/grade(s) taught, subjects taught	Teacher/Principal
4	School management	PTA meetings, number of students, number of teachers, school meal programs, extracurricular activities	Teacher/Principal
5	Perceptions and beliefs about adolescent issues	Important subjects, student attendance, student nutrition/diet, WASH, teacher support	Teacher/Principal
6	Nutrition activities in school	Involvement with nutrition-related activities/interventions	Teacher/Principal
7	Health and nutrition knowledge	Nutrition knowledge, WASH knowledge	Teacher/Principal
8	Training exposure	Exposure to and training received on adolescent nutrition	Teacher/Principal
9	Supervision	Supervision received from superiors, woreda school supervisors, etc.	Teacher/Principal

#### 4.1.3 HEW questionnaire

Interviews with HEWs at the primary schools will gather information on the individual's role at the school and in communities, nutrition-related activities, nutrition knowledge, exposure to training, and supervision.

Table 7. Description of modules in the HEW questionnaire

Module	Topic	Description	Respondent
1	Identification	Location, health post	Enumerator
2	Demographic characteristics	Age, education, years of experience and other characteristics of the HEW	HEW
3	Time commitments and workload	Types and frequency of activities or interactions with school and parent-teacher association, content/topics discussed	HEW
5	Health and nutrition knowledge	Knowledge and importance of proper nutrition for adolescent girls	HEW

7	Perceptions and beliefs about adolescent issues	Perceptions and beliefs about adolescent issues (e.g. health, nutrition, WASH) in the kebele	HEW
8	Training exposure	Exposure to and training received on adolescent nutrition	HEW
9	Supervision and contact with other actors	Frequency and content of supervision on adolescent nutrition services/activities	HEW

Note: The HEW interview for the Adolescent Nutrition study will be conducted at the same time as the HEW interview for the Alive & Thrive Ethiopia 3.0 Maternal Nutrition study. There is one questionnaire for both studies, therefore only the modules relevant to the Adolescent Nutrition study are included above.

#### 4.1.4 Adolescent girl questionnaire

Interviews with adolescent girls will be conducted at baseline and endline and gather information on school attendance, exposure to nutrition information, dietary diversity, meal and snacking habits, WASH practices, health and health seeking behaviors, health and nutrition knowledge, food security, home food environment, parental interactions, social desirability, gender and marriage beliefs and decision-making power, and anthropometry.

Table 8. Description of modules in the adolescent girl questionnaire

Module	Topic	Description	Respondent
1	Identification	School and grade of adolescent	Enumerator
2	Adolescent and family background	Age, DOB, grade level, language, characteristics of mother/father	Adolescent
3	School attendance	Attendance, reasons for absences, extracurricular activities, class performance	Adolescent
4	Exposure to nutrition information	Exposure to adolescent nutrition and/or WASH information at school and outside of school, and exposure to media and food/drink advertisements	Adolescent
5	Dietary diversity	Dietary diversity of the adolescent in the past 24 hours	Adolescent
6	Meal and snacking habits	Meals/snacks taken during school days, foods consumed before and during school, access to food vendors near school grounds	Adolescent
7	WASH practices	Handwashing, drinking water, food hygiene, menstruation	Adolescent
8	Health and health seeking behaviors	Illness, health seeking behaviors, weight and body image	Adolescent
9	Health and nutrition knowledge	General knowledge of health and nutrition, including WASH and importance of various macro and micronutrients	Adolescent
10	Home food environment	Availability of foods at home	Adolescent

11	Food security	Prevalence of household hunger using the FANTA household food insecurity access scale (HFIAS)	Adolescent
12	Parent-adolescent interactions	Relationship and interactions with parents, and perceptions of parents' monitoring of food and eating habits	Adolescent
13	Social desirability	Desire for social approval	Adolescent
14	Gender, marriage beliefs and decision-making power	Opinions about girls' and boys' education, marriage and household roles, and decision-making power in the household	Adolescent
15	Anthropometry	Weight and height measurements	Adolescent

#### 4.1.5 Parent questionnaire

Interviews with parents of adolescent girls will be conducted at baseline and endline and gather information on school involvement, exposure to nutrition information, dietary diversity, health and nutrition knowledge, food security, home food environment, social desirability, gender and marriage beliefs and decision-making power, dwelling and assets.

Table 9. Description of modules in the adolescent girls' parents' questionnaire

Module	Topic	Description	Respondent
1	Identification	School and respondent type	Enumerator
2	Household roster	Information on composition of the household, including designation of the head of household, a list of all household members, their ages and sex, and their relationship to the adolescent girl, and the highest educational level attained and activity/employment in the past month of all household members at least 15 years of age	Parent
3	School involvement	School fees, and participation in parent-teacher association, school management committee and teacher meetings	Parent
4	Exposure to nutrition information	Exposure to adolescent nutrition and/or WASH information, and exposure to media and food/drink advertisements	Parent
5	Dietary diversity	Dietary diversity of the adolescent and household in the past 24 hours	Parent
6	Home food environment	Availability of foods at home	Parent
7	Health and nutrition knowledge	General knowledge of health and nutrition, including WASH and	Parent

		importance of various macro and micronutrients	
8	Parent-adolescent interactions	Relationship and interactions with adolescent, monitoring of food and eating habits, adolescent weight and body image	Parent
9	Social desirability	Desire for social approval	Parent
10	Gender, marriage beliefs and decision-making power	Opinions about girls' and boys' education, marriage and household roles, and decision-making power in the household	Parent
11	Food security	Prevalence of household hunger using the FANTA household food insecurity access scale (HFIAS)	Parent
12	Dwelling	House construction (materials used for floor, walls, and roof), availability of water and electricity, sources of fuel/energy for cooking, WASH facilities	Parent
13	Assets	Ownership of durable household goods (in working condition), including tools for agricultural production	Parent

#### 4.2 COVID-19 precautionary measures

Since early 2020, close-range contacts between enumerators and study participants during data collection activities present a particular risk for spreading COVID-19 in communities with vulnerable populations. The collaborating survey firm, Addis Continental Institute of Public Health (ACIPH), has developed formal fieldwork guidelines based on directives for the prevention and control of the COVID-19 pandemic by the Ministry of Health (MOH) and Ethiopian Public Health Institute, and UNICEF recommendations for surveilling and monitoring nutrition in the context of COVID-19. As part of the guidelines, all enumerators and study participants will wear masks (provided to them) and wash or sanitize their hands before and after each interview. Interviews will be conducted outside or in a well-ventilated space and enumerators will maintain two meters of distance from the interviewee and other household members. Measuring boards and scales will be sanitized after every anthropometric measurement. Any study staff with COVID-19-related symptoms (fever, dry cough, extreme fatigue, respiratory problems or any unusual illness) will be immediately excluded from fieldwork and remain isolated as per MOH guidelines. Any study participants with COVID-19-related symptoms will be excluded from the study and advised to remain isolated and seek appropriate services according to MOH and any local guidelines.

All survey staff will be assessed for COVID-19-related symptoms each day before enumerator training begins, and field supervisors will assess enumerators each day before starting data collection. In addition, Co- and Principal Investigators of the project will be in daily contact with ACIPH and in-country partners during data collection to assess the changing risks and government measures.

### 4.3 Data management

A secure data file structure will be established in an IFPRI-server-based Dropbox Professional folder for use by the IFPRI research team and potential collaborators. Original, sensitive (non-anonymized) data files and documents will be stored in a folder with access restricted to senior IFPRI researchers. A do file will be written to anonymize survey data files and export the anonymized data to a shared Dropbox folder for data cleaning and analysis by research support staff and other project team members.

All changes to the raw data output files from the Computer-Assisted Personal Interviews (CAPI) software will be recorded. Formatting, reshaping, and labeling of data will be documented using detailed and well-annotated do files.

### 4.4 Statistical methods

Data analysis will use econometric analysis to control for (any) differences at baseline and between intervention and comparison groups for all relevant variables of interest. Statistical testing for differences between the two groups will be done using a random effects regression, accounting for the clustering of errors within and across schools.

The randomized study design allows for the identification of causal effects of the adolescent nutrition intervention through comparisons of mean outcomes between the treatment and control groups. Key indicators will include dietary diversity. Impact will be assessed using “difference-in-difference” (DID) estimation and/or analysis of covariance (ANCOVA) controlling for covariates. Data management, data cleaning and statistical analyses will be conducted using Stata version 16 (Statacorp, USA). The statistical significance for tests will be set at 5% for main effects or 10% in case of interactions. All statistical tests will be one-sided.

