### III. Statistical Analysis Plan

#### 3.1 General principles and methods

Data analyses will be performed using STATA version 17.0 (StataCorp LLC). All applicable statistical tests will be two-sided to allow potential findings of unexpected effects. Statistical significance will be presented at levels of  $p<0.05$ ,  $p<0.01$ , and  $p<0.001$ .

A diagram presenting the flow of clusters and individuals through the trial, based on the Consolidation Standard of Reporting Trials (CONSORT) statement: extension to cluster randomized trials (1,2), is shown as follows.

[figure not shown]

Figure 1. CONSORT flow diagram for repeated cross-sectional surveys

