### 3.3 Impact estimates

The main analysis of impacts will be performed using intent-to-treat (ITT) specifications, wherein all study participants in the originally assigned program group at baseline are included in the statistical analysis and analyzed according to their program group, regardless of whether they received interventions or not. Respondents who refused or withdrew consent or those who are ineligible according to study protocol are excluded from ITT analysis.

The main impacts of the interventions will be estimated for: (1) dietary diversity score, (2) consumption of unhealthy foods/junk foods, and (3) meal frequency. Secondarily, impact will be estimated for exposure to the core interventions: classroom lessons about adolescent nutrition and healthy diets, flag ceremonies/assemblies to remind about key healthy eating messages, adolescent girls club/student peer mentoring on adolescent nutrition, and parent-teacher meetings to educate parents about adolescent nutrition and healthy diets. All impact indicators will be assessed among adolescent girls, except for the exposure to parent-teacher meetings which will be assessed from parents.

Given that the main impact indicators with full sample sizes were collected at endline only, linear regression models will be used to test the means of the outcome for estimates of group differences (intervention vs. control) at endline, with standard errors clustered at the school level. In the adjusted models, we will control for covariates such as adolescent girl age and other variables that differed between study arms. Robustness tests will be conducted using difference-in-differences analysis where outcome variables exist at baseline.

Table 6. Dummy table for impact estimates

Indicator	Baseline		Endline		Unadjusted impact est. 	Adjusted impact est. 
	A&T (N=)	Control (N=)	A&T (N=)	Control (N=)		
	Percent/Mean (SD)	Percent/Mean (SD)	Percent/Mean (SD)	Percent/Mean (SD)		
Dietary diversity score						
Consumption of unhealthy foods						
Meal frequency						

Controlling for clusters by school only.

Adjusted for AG age, household food security and wealth tertile, and clustered by school.

\*\*\* p<0.01; \*\* p<0.05; \* p<0.1

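### Protocol 4.4 names difference-in-differences and/or ANCOVA as the impact estimator, but the stated 0.5 food-group detectable difference does not hold for difference-in-differences, and SAP 3.3 makes a different analysis the main one

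*Protocol*

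**What the plan says.** **Sample size.** Protocol 2.6 plans 270 girls per arm at endline, 10 from each of 27 schools. Using the SD of 1.56 seen at baseline and an ICC of 0.015, it says "we estimated that this sample size will detect a minimum difference of 0.5 food groups". Table 3 gives 81 girls per arm at baseline, which is 3 per school, and the text describes this as a light subsample for checking that the arms are comparable. Neither document gives a detectable difference for DID.

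**Protocol analysis.** Section 4.4 lists the impact methods as "DID) estimation and/or analysis of covariance (ANCOVA) controlling for covariates" and names no primary one. It adds that "Statistical testing for differences between the two groups will be done using a random effects regression". On the error rate it says "The statistical significance for tests will be set at 5% for main effects" and "All statistical tests will be one-sided".

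**SAP analysis.** Section 3.3 notes that full samples of the main indicators exist only at endline. It therefore says that "linear regression models will be used to test the means of the outcome for estimates of group differences (intervention vs. control) at endline". The model allows for school clustering through its standard errors. DID has a secondary role: "Robustness tests will be conducted using difference-in-differences analysis where outcome variables exist at baseline". On sidedness, SAP 3.1 says "All applicable statistical tests will be two-sided to allow potential findings of unexpected effects".

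**The concern.** For one primary outcome, the protocol and the SAP name different main estimators and different test directions. The protocol's wording also leaves open which of its two methods would decide the result.

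DID subtracts a baseline difference that is itself estimated, here from 81 girls per arm, so it carries that sampling error on top of the endline error. A detectable difference worked out for the endline comparison cannot be carried over to it.

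Two things are at stake. A reader of the protocol alone would attach the 0.5 figure to a method that does not achieve it. A reader of the SAP would see DID offered as a robustness test with no warning that it is much less precise than the analysis it is meant to support.

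**Working it through.** **Inputs from the documents.** SD 1.56, ICC 0.015, 80% power and 5% significance; 27 schools per arm; 270 girls per arm at endline (10 per school) and 81 at baseline (3 per school). **Assumed, because not given:** the correlation of the school effect between rounds (CAC), taken from 0 to 1. All figures use the normal approximation. Multipliers are 1.960 + 0.842 = 2.802 two-sided and 1.645 + 0.842 = 2.487 one-sided.

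**1. The protocol's first figure, 189 per group for 0.6 food groups (SD 1.40, ICC 0.18).**
- Without clustering, two-sided: n = 2 × (1.40 × 2.802 / 0.6)² = 85.5.
- With 27 schools fixed: 85.5 × 0.82 / (1 − 85.5 × 0.18 / 27) = 162.9, or 6.03 per school. Rounded up to 7, 27 × 7 = 189, which reproduces.
- One-sided, the same steps give 100.2, or 4 per school and 108 girls. The planning arithmetic therefore appears to be two-sided.

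**2. The protocol's second figure, 0.5 food groups with 270 per arm.**
- Design effect: 1 + 9 × 0.015 = 1.135.
- SE of the difference: 1.56 × √(2 × 1.135 / 270) = 0.143.
- Detectable difference: 2.802 × 0.143 = 0.40 two-sided (0.41 with t on 52 df), 0.36 one-sided.
- Power for 0.5: Φ(0.5/0.143 − 1.960) = 94% two-sided, 97% one-sided.

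The stated 0.5 is not reproduced; its inputs give 0.40. It is conservative for an endline-only comparison.

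**3. DID.** Variance components per arm:
- Endline: 1.56² × 1.135 / 270 = 0.01023.
- Baseline: 1.56² × (1 + 2 × 0.015) / 81 = 0.03095.
- Covariance of the two school-level means: CAC × 0.015 × 1.56² / 27 = CAC × 0.00135.

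SE = √(2 × (endline + baseline − 2 × covariance)).

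| | SE | Detectable, two-sided | Power for 0.5, two-sided | Detectable, one-sided | Power for 0.5, one-sided |
|---|---|---|---|---|---|
| Endline only | 0.143 | 0.40 | 94% | 0.36 | 97% |
| DID, CAC = 1 | 0.277 | 0.78 | 44% | 0.69 | 56% |
| DID, CAC = 0 | 0.287 | 0.80 | 41% | 0.71 | 54% |

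The baseline term is about three times the endline term, so most of the DID variance comes from the small baseline.

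**4. Sensitivity to re-interviewed girls.** Protocol 2.6 says that the endline sample includes the girls seen at baseline. If all 81 per arm were re-interviewed, with an assumed within-girl correlation r, the DID variance falls by 4 × 1.56² × 0.985 × r / 270.
- CAC = 0, r = 0.2 to 0.4: detectable difference 0.77 to 0.73 two-sided, 0.68 to 0.65 one-sided.
- The two favourable extremes together (CAC = 1, r = 0.4): variance 0.0769 − 0.0142 = 0.0627, SE 0.250, detectable difference 2.802 × 0.250 = 0.70 two-sided, power for 0.5 about 51%.

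DID does not reach 0.5 in any of these cases.

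**The case against.** **The SAP has already dealt with this.** It fixes one main analysis, gives a sound reason for it and limits DID to robustness. That fits a sample size built on the endline and a baseline meant only to check comparability. This stands. A reader might infer from Protocol 4.4 that the trial is badly underpowered for its primary outcome. The documents do not support that, because the SAP's main analysis has 94% two-sided power for 0.5 at the stated ICC. What remains is a protocol section that disagrees with the SAP, and a robustness test with no guidance on how to read it.

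**The size depends on the test direction.** This also stands. The 0.78 to 0.80 range follows the SAP's two-sided rule. Under the protocol's own one-sided rule, DID detects 0.69 to 0.71. Both exceed 0.5, but neither should be quoted without its rule.

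**Random-effects regression is not a rival estimator.** Correct. It is a way to handle clustering, and either DID or ANCOVA can be fitted with it. A reader might count three competing primary analyses; the text supports only an unresolved choice between two in the protocol, and a different one in the SAP.

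**Nothing makes DID decisive.** Also correct. Neither document says that a non-significant DID would overturn the result. The risk is one of interpretation, not of a stated decision rule.

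**A higher ICC would change the comparison.** It would, but the protocol pairs its earlier ICC of 0.18 with SD 1.40 and its later SD of 1.56 with ICC 0.015. Crossing the two is not a scenario the protocol presents, so no conclusion here rests on it.

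**Conclusion.** The point holds as a conflict between documents and a mismatch between a stated detectable difference and a named estimator. It does not show that the trial's main analysis is too small.

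At SD 1.56 and ICC 0.015, DID with 81 baseline girls per arm has a standard error about 1.9 to 2.0 times that of the endline comparison (0.277 to 0.287 against 0.143). Treating the two rounds as different girls, a two-sided DID would miss a true difference of 0.5 in 56 to 59% of trials. If every baseline girl were re-interviewed and both assumed correlations were favourable, it would still miss it about half the time.

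The conclusion rests on the protocol's SD and ICC, the normal approximation and the assumed range for school autocorrelation. Adequate power for the SAP's main analysis likewise rests on the ICC of 0.015.

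**What to change.** 1. In Protocol 4.4, replace the DID and/or ANCOVA wording with the SAP 3.3 endline regression with school-clustered standard errors, and bring the random-effects sentence into line with it.
2. State one rule on one-sided or two-sided testing in both documents. The 189-per-group calculation reproduces only two-sided.
3. Add woreda, the randomisation stratum named in Protocol 3.1, to the model in both documents. This is an addition to SAP 3.3. With seven woredas it uses six terms, a small cost with 54 schools.
4. Label DID supportive in both documents and give its own detectable difference, about 0.8 food groups two-sided at ICC 0.015.
5. State that a non-significant DID does not by itself overturn the primary result, and report its estimate and confidence interval beside the primary one.

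A school baseline mean is not proposed as a covariate. It would rest on 3 girls per school, and its reliability at ICC 0.015 is only 3 × 0.015 / 1.03 = 0.04.

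The cost is wording in two documents and a few degrees of freedom. No new data are needed.

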### 6.2 Protocol amendments

All amendments to the protocol will be reported (by IFPRI Co-Investigators and ACIPH Co-Investigator) to and agreed upon with Alive & Thrive. Substantive changes to the protocol that may impact the safety of participants or the scientific validity, scope, or ethical rigor of the study will be reviewed by the IFPRI IRB.

Version control using protocol version identifiers and dates will be used to track the history of amendments and identify the most recent protocol version.

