### 2.1 Research question 1 (impact on diets of adolescent girls)

For impact estimates, outcome measures related to adolescent diet will be used from the AG dataset only.

Table 2. Outcome measures for RQ1

Outcome	Indicator	Data source
Dietary diversity, consumption of unhealthy foods, and meal frequency	
Primary outcome:
 
 
- Dietary diversity score (# of food groups, out of 10 groups)
 
 
Secondary outcomes:
 
 
- % AG consumed unhealthy foods in past 24h (i.e., sweet foods and sweets, fried and salty foods, and sugar-sweetened beverages)
 
- Mean meal frequency score (# meals or snacks, out of 6 times)
 
	AG survey

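### The protocol makes every test one-sided at 5% and the SAP makes them two-sided, so a favourable primary result with z between 1.645 and 1.960 is significant under one document and not under the other

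*Protocol*

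**What the plan says.** Protocol 4.4 gives the level and the direction of testing in adjacent sentences: "The statistical significance for tests will be set at 5% for main effects or 10% in case of interactions", followed by "All statistical tests will be one-sided". It names no direction and gives no reason. The same section lets impact be assessed by difference-in-differences (DID), by ANCOVA, or by both.

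SAP 3.1 states: "All applicable statistical tests will be two-sided to allow potential findings of unexpected effects". It continues, "Statistical significance will be presented at levels of" p<0.05, p<0.01 and p<0.001. It does not mention the protocol's one-sided rule or describe its own rule as a change.

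SAP 3.3 contains dummy Table 6 for the impact estimates. Its first row is the dietary diversity score, the SAP's single primary outcome. The star key there is p<0.1, p<0.05 and p<0.01, which is not the set given in SAP 3.1.

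Protocol 2.6 plans for 80% power at alpha 0.05 without giving the number of sides: "We calculated that a minimum sample of 189 girls per group will be able to detect a minimum of 0.6 food group consumption increase".

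Protocol 6.2 covers changes to the protocol: "All amendments to the protocol will be reported" to and agreed with Alive & Thrive, and substantive ones go to the IFPRI IRB.

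**The concern.** SAP section II says the primary outcome is the basis for deciding on overall study impact, so the rule for calling it significant has to be unique. Here it is not. Take a favourable difference with two-sided p of 0.07. Under the protocol it is significant (one-sided p 0.035), under SAP 3.1 it is not, and in Table 6 it carries a star. With no order of precedence, the conclusion could be settled after the result is known.

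Two further consequences follow. A one-sided test for benefit cannot declare an unfavourable effect, which is what the SAP says it wants to be able to find. In addition, the impact estimate in a DID model is an arm-by-round interaction. Read literally, Protocol 4.4 would allow that term to be tested at one-sided 10%, a critical z of about 1.28.

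**Working it through.** **1. Which rule does the planned sample size fit?** Inputs from Protocol 2.6 and 3.1: SD 1.40, difference 0.6, ICC 0.18, power 80% (z = 0.8416), 27 schools per arm.

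Per-arm size without clustering: A = 2 × (z_alpha + 0.8416)² × 1.40² / 0.6².

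With m girls per school, 27m = A × (1 + (m − 1) × 0.18), so m = A × 0.82 / (27 − 0.18A).

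| | z_alpha | A | m | rounded up | per arm |
|---|---|---|---|---|---|
| Two-sided 5% | 1.960 | 85.47 | 6.03 | 7 | 27 × 7 = 189 |
| One-sided 5% | 1.645 | 67.32 | 3.71 | 4 | 27 × 4 = 108 |

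The protocol's 189 is reproduced exactly with a two-sided test. Rounding up is needed: 6 girls per school gives 79.9% power and 7 gives 82.4%. The one-sided calculation by the same route gives 108 (power 81.4%). Because the protocol does not state the sides, this is an inference about what the designers used.

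The updated calculation does not help. With 270 per arm, SD 1.56 and ICC 0.015, the detectable difference is 0.40 two-sided and 0.36 one-sided. Neither is the stated 0.5.

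**2. Where do the two rules disagree?** For a favourable result:

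| z | one-sided p | two-sided p |
|---|---|---|
| 1.645 | 0.050 | 0.100 |
| 1.80 | 0.036 | 0.072 |
| 1.960 | 0.025 | 0.050 |

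With a t reference on 53 degrees of freedom (54 schools), the limits become 1.674 and 2.006.

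**3. The zone in food groups.** For an endline comparison of 270 per arm with 10 girls per school, SE = 1.56 × sqrt(2 × (1 + 9 × ICC) / 270).

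- ICC 0.015: design effect 1.135, SE 0.1430. Zone: 1.645 × 0.1430 = 0.235 to 1.960 × 0.1430 = 0.280.
- ICC 0.18: design effect 2.62, SE 0.2173. Zone: 0.357 to 0.426.

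**4. Chance of landing in the zone.** For a true difference d, this is Phi(1.960 − d/SE) − Phi(1.645 − d/SE).

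| True difference | ICC 0.015 | ICC 0.18 |
|---|---|---|
| 0.3 | 12.0% | 11.5% |
| 0.4 | 7.7% | 12.5% |
| 0.5 | 3.0% | 11.1% |

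With no true effect the chance is 2.5%. That is the gap between a false favourable claim rate of 5% (protocol) and 2.5% (SAP).

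**The case against.** The strongest reply is that the SAP simply supersedes the protocol. It reads as the later document: it describes the endline survey in the past tense and names a newer Stata version. It also gives a reason for two-sided testing and is the stricter of the two. On that view, what remains is stale protocol text. This supports two-sided testing as the repair, but it does not settle precedence. Nothing in the body of either document says that the SAP overrides Protocol 4.4. Because the SAP text was written after endline collection, a reader could equally defend the protocol as the rule fixed beforehand. Title pages were not in the text reviewed, so a version statement there cannot be excluded.

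The sample-size inference is not strictly unique. A one-sided route also reaches 189: 67.32 × (1 + 10 × 0.18) = 188.5, rounded up. That needs the design effect for 11 girls per school, or for 10 per school with m used in place of m − 1, whereas 189 is 27 schools of 7. The two-sided route is the natural one, and the contradiction does not depend on it.

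The size estimates assume the same estimator and SE under both rules, although the documents differ. SAP 3.3 uses endline-only regression, while the protocol allows DID. With 81 baseline girls per arm (3 per school), SD 1.56, ICC 0.015 and no school-level correlation between rounds, the DID SE is 1.56 × sqrt(2 × 1.135/270 + 2 × 1.03/81) = 0.287, and the zone moves to about 0.47 to 0.56. The ICC 0.18 line varies the ICC alone; in the protocol that value went with SD 1.40 on nine food groups. With SD 1.40 the zone is 0.321 to 0.382. These points change where the zone lies, not whether it exists.

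Finally, the Table 6 key is only a display convention. That is true, but it sits on the primary outcome and marks as notable a result that SAP 3.1 would not.

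**Conclusion.** The concern holds, and the plan is wrong as written: two current statements on the sidedness of every test contradict each other, and the primary outcome is affected. The disputed zone is z from 1.645 to 1.960, or 0.235 to 0.280 food groups on the updated planning inputs. The chance of a result there ranges from about 3% to about 12% for true differences between 0.5 and 0.3 at ICC 0.015, and is about 11% to 13% at ICC 0.18. The figures rest on a normal approximation and on one endline estimator with the same SE under both rules. The contradiction itself rests only on the two texts. It must be fixed before a primary conclusion is drawn.

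**What to change.** Adopt one rule in both documents: two-sided tests, 5% for main effects.

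- In Protocol 4.4, replace the one-sided sentence with: *All statistical tests will be two-sided.*
- Keep the 10% level for interactions, but state that the DID impact term (arm by survey round) is tested at 5%.
- In SAP Table 6, change the star key to * p<0.05, ** p<0.01, *** p<0.001, and drop the p<0.1 star.

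The cost is a protocol amendment under section 6.2, agreed with Alive & Thrive and reviewed by the IFPRI IRB if judged substantive, plus one SAP footnote. A SAP sentence stating that 3.1 replaces Protocol 4.4 on sidedness, reported as a change, would resolve that conflict. It would leave the protocol text uncorrected and would not deal with the DID level or the star key. No new data are needed. The price is that results with two-sided p between 0.05 and 0.10 can no longer be called or marked significant.
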